8.5.1	Investigator reporting: notifying the Dartmouth IRB	18
8.6	UNBLINDING PROCEDURES	189
8.7	STOPPING RULES	189
8.8	MEDICAL MONITORING	199
9	DATA HANDLING AND RECORD KEEPING	20
9.1	CONFIDENTIALITY	20
9.2	SOURCE DOCUMENTS	20
9.3	RECORDS RETENTION	20
10	ETHICAL CONSIDERATIONS	20
11	STUDY FINANCES	21
11.1	FUNDING SOURCE	21
11.2	CONFLICT OF INTEREST	21
11.3	SUBJECT STIPENDS OR PAYMENTS	21
12	REFERENCES	21
13	ATTACHMENTS	23

List of Abbreviations

DLPFC – Dorsolateral Prefrontal Cortex
EEG – Electroencephalogram
EPs – Evoked Potentials
IAPS – International Affective Pictures Set
LF TMS – Low Frequency Transcranial Magnetic Stimulation
MINI - Mini-International Neuropsychiatric Interview
MOCA - Montreal Cognitive Assessment
MT - Motor Threshold
PANAS - Positive and Negative Affect Schedule
QIDS – Quick Inventory of Depressive Symptomatology-Subject Rated and Visual Analog Scale
QOL – Quality of Life
SAFTEE – Systematic Assessment for Treatment Emergent Events
TLE – Temporal Lobe Epilepsy

Study Summary

Title	Safety and Feasibility of Accelerated Low-Frequency Transcranial Magnetic Stimulation for Medication-Resistant Depression in Patients with Epilepsy
Short Title	TMS for Depression in Patients with Epilepsy
Protocol Number	N/A
Phase	Phase 2
Methodology	Non-randomized, non-controlled
Study Duration	11/1/2015 – 10/31/2020
Study Center(s)	DHMC, Lebanon, NH DHMC, Manchester, NH (Recruitment)
Objectives	Primary objective is to determine whether it is safe and feasible to administer low-frequency right frontal lobe transcranial magnetic stimulation using an accelerated protocol to treat depression in patients with focal epilepsy.
Number of Subjects	20
Diagnosis and Main Inclusion Criteria	Epilepsy and moderate symptoms of depression
Study Product, Dose, Route, Regimen	MagVenture transcranial magnetic device with a figure 8 coil, delivered in 15 50-minute trains of 1 Hz; 45,000 total pulses; stimulation intensity between 80-120% of patient's motor threshold
Duration of administration	3 days
Reference therapy	None
Statistical Methodology	

1 Introduction

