1.5 Dose Rationale and Risk/Benefits

Low-frequency (LF) TMS refers to TMS delivered at a frequency of 1 Hz or below. Unlike HF TMS, LF TMS can decrease cortical excitability and may have anticonvulsant effects[42]. Low frequency TMS applied to right DLPFC also has an extensive though smaller database supporting its antidepressant efficacy, and comparisons to left HF DLPFC TMS suggest both treatments work equally as well[43, 44]. Surprisingly, LF TMS has not been investigated as an antidepressant treatment in patients with epilepsy, though it would have clear advantages compared to HF TMS including increased tolerability and potentially anticonvulsant effects.

2 Study Objectives

Specific Aim 1: To examine the safety and feasibility of accelerated low-frequency transcranial magnetic stimulation (TMS) to the right dorsolateral prefrontal cortex in patients with epilepsy and comorbid depression.

Hypothesis 1.a. (safety): Treatment will not produce serious adverse events defined as an increase in seizure rate or hospitalization.

Hypothesis 1.b. (safety): Treatment will not be associated with a higher rate of adverse events as measured by a modified Systematic Assessment for Treatment Emergent Events (SAFTEE) given at baseline and immediately post-TMS.

Hypothesis 1.c. (feasibility): At least 80% of participants will complete the study protocol.

Specific Aim 2: To examine the utility of electrophysiological and behavioral profiles as biomarkers of depression correlated with response to treatment with right-DLPFC TMS in patients with epilepsy.

Hypothesis 2a: Changes in dense array EEG based biomarkers of depression (hemispheric frontal alpha power asymmetry, anterior cingulate theta power, and frontotemporal alpha coherence) will correlate with changes in depression scores.

3 Study Design

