3.2 Primary Study Endpoints

1. Change in weekly seizure rate as assessed by self-report seizure log.
2. Change in significant side effects as assessed by the Systematic Assessment for Treatment Emergent Events (SAFTEE)[50].
3. Feasibility of participation such that 80% of patients will complete the study protocol including all measures, MRI, dense array EEG, and TMS.
4. Correlation of pre and post TMS hemispheric frontal alpha power asymmetry, anterior cingulate theta power, and frontotemporal alpha coherence with changes in depression severity.

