4.3.2 Data Collection and Follow-up for Withdrawn Subjects

Should a subject be withdrawn prematurely from the study, follow-up will continue to be attempted as planned based on protocol: subjects will complete assessments immediately following discontinuation of TMS, one week after last TMS treatment, one month after last TMS treatment, and three months after last TMS treatment. For a subject to be considered “lost to follow-up,” they must at a minimum fail to respond to 3 consecutive attempts at communications from study team (email and phone contact). Follow-up will not occur if a subject refuses to participate in follow-up assessments.

5 Study Device

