5.2 Method for Assigning Subjects to Treatment Groups

All 20 patients with epilepsy and depression will be enrolled into the treatment group. All patients will have dense array EEG and MRI.

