7.1 Statistical Methods

The study will be closely monitored for safety parameters with stopping rules as defined in Section 8.7. At the conclusion of the study, baseline demographics and clinical characteristics will be summarized with means, proportions and associated standard deviations. For safety, occurrence rates of SAE (seizures or hospitalizations) will be estimated and exact binomial confidence intervals will be formed. Very few if any are expected in this small study. The SAFTEE scale will be compared before and after TMS with independent t-tests based on the individual changes from baseline. The study completion rates will be estimated and compared to the target rate of 80% using exact tests for binomial data.

The secondary outcomes will be measured before and after treatment using dense-array EEG biomarkers and depression scores along with test results during functional MRI and EEG. Paired t-tests will be used to compare *change* in depression severity, memory, executive functioning, quality of life, and social cognition from baseline to endpoint. MRI patterns of activation will be analyzed. Analysis of variance for repeated measures will be used to test task and neuropsychological testing results.

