7.2 Sample Size Determination

For the primary safety outcomes, we consider the expected upper limit of a one-sided 90% exact confidence interval for the proportion with an SAE based on a sample size of 20. If the underlying rate is 0.05, the upper limit is 0.131. This increases to 0.145 if the underlying rate is 0.10.

For the secondary outcomes comparing baseline to endpoint depression measurements, a two-sided paired t-test with a significance level of 0.05 and a power of 0.90 can detect a difference of .764 standard deviations of the changes from baseline.

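### Section 7.1 names an independent t-test for SAFTEE, a primary endpoint measured before and after TMS in one group; the test should be called paired

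*Combined protocol and SAP*

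**What the plan says.** Section 7.1 gives the only analysis of SAFTEE in the available text: "The SAFTEE scale will be compared before and after TMS with independent t-tests based on the individual changes from baseline".

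The Study Summary describes the design as "Non-randomized, non-controlled", and section 5.2 adds: "All 20 patients with epilepsy and depression will be enrolled into the treatment group". Section 3.2 lists as its second primary endpoint "Change in significant side effects as assessed by the Systematic Assessment for Treatment Emergent Events (SAFTEE"). Hypothesis 1.b in section 2 has the scale "given at baseline and immediately post-TMS".

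For the other before-after outcomes the plan names a different test. The second paragraph of section 7.1 begins a sentence on depression severity, memory, quality of life and other measures with "Paired t-tests will be used to compare". Section 7.2 bases its depression calculation on a two-sided paired t-test at the 0.05 level with 90% power, which it says "can detect a difference of .764 standard deviations of the changes from baseline".

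**The concern.** An independent-samples t-test compares two separate sets of people, and this trial has one. If the within-patient changes are the data, there is no second group to compare them with. If the before and after scores are treated as two samples, the test can be computed, but it ignores that the same patients produced both. The sentence therefore names one kind of test and describes the data for another.

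The wording matters because it governs a primary safety endpoint. Secondary outcomes in the same section get paired tests, so a reader could take the contrast as deliberate. Scores from one patient on two occasions are usually positively correlated, and a test that ignores this uses too large a standard error. In a safety study that error runs the wrong way: a real rise in side effects is harder to detect, and Hypothesis 1.b, which expects no increase, is easier to declare supported.

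**Working it through.** **Inputs from the plan.** n = 20 (section 5.2). Two-sided alpha 0.05, power 0.90 and a detectable difference of 0.764 SD of the changes (section 7.2). These last three are stated for depression; the plan gives no such figures for SAFTEE, so they are borrowed here for illustration.

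**Assumed input.** The correlation ρ between a patient's before and after scores is not in the documents. Values of 0, 0.3, 0.5 and 0.7 are used.

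**Step 1: reproduce the plan's figure.** A paired t-test is a one-sample t-test on the changes, with 19 df and critical value 2.093. The noncentrality is 0.764 × √20 = 3.417. The noncentral t distribution then gives power 0.8997, which agrees with the stated 0.90. The exact detectable difference at 90% power is 0.7645 SD.

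**Step 2: compare standard errors.** Let each score have SD σ.

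- Paired: SE = σ√(2(1−ρ)/n).
- Two-sample on before and after scores: SE is about σ√(2/n).
- Ratio, two-sample to paired: 1/√(1−ρ), which is 1.195, 1.414 and 1.826 at ρ = 0.3, 0.5 and 0.7.

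The two-sample statistic for the same true change is therefore centred near 3.417 × √(1−ρ), or 2.86, 2.42 and 1.87, against a critical value of 2.024 (38 df).

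**Step 3: exact error rates for bivariate normal scores.** Take σ = 1. The mean change is normal with mean δ and variance 2(1−ρ)/n. The two sample variances satisfy 19(s₁² + s₂²) = (1+ρ)A + (1−ρ)B, where A and B are independent chi-square variables with 19 df. The test rejects when |mean change| / √((s₁² + s₂²)/20) exceeds 2.024. Setting δ = 0 gives type I error, and δ = 0.764 × √(2(1−ρ)) gives power. Numerical integration gives:

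| ρ (assumed) | Two-sample type I error | Two-sample power | Paired type I error | Paired power |
|---|---|---|---|---|
| 0 | 0.0500 | 0.915 | 0.05 | 0.900 |
| 0.3 | 0.0208 | 0.835 | 0.05 | 0.900 |
| 0.5 | 0.0075 | 0.706 | 0.05 | 0.900 |
| 0.7 | 0.0010 | 0.415 | 0.05 | 0.900 |

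**Step 4: check that normality does not drive the result.** Side-effect scores may behave like skewed counts. Poisson counts sharing a gamma patient effect were simulated, with 100,000 runs per cell and assumed means of 3 and 8 per patient. At ρ = 0.3, 0.5 and 0.7 the two-sample results were:

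- Mean 3: type I error 0.0199, 0.0076, 0.0013; power 0.860, 0.769, 0.573.
- Mean 8: type I error 0.0220, 0.0076, 0.0010; power 0.851, 0.748, 0.515.

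The paired test in the same runs had type I error 0.047–0.050 and power 0.899–0.902. The direction is the same.

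**Step 5: the other reading.** If the individual changes are analysed, a t-test on them in one arm is the paired test, and the loss is zero.

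**The case against.** The strongest reply is that the sentence already specifies the right analysis. It says the tests use each patient's change from baseline, and in one arm a t-test on those changes is the paired t-test. The error rates above belong to a reading that drops half the sentence, and they rest on an assumed correlation and on an effect size given for depression. This largely stands: the analysis of changes is the likelier reading, the expected effect on results is nil, and the figures describe only the unlikely case. It does not rescue the label, because the named test is not valid for this design.

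A second reply is that the plural may loosely mean separate tests at several time points. The text does not say so, and each such test would still be paired.

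A third is that patients are protected in any case. That is correct. Individual discontinuation (section 4.2.1), adverse-event recording (section 8.4) and the stopping rules (section 8.7) do not use this test, and the sample size does not depend on SAFTEE. What is at stake is only the reported result for the endpoint.

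The available text also leaves open which of the two SAFTEE assessments before TMS (Visits 1b and 3) is the baseline, and how patients who use the optional fourth treatment day are handled. The table cited in section 3.3 and the attachments listed in section 13 are not in the available text and may settle both, so these points carry no weight here.

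**Conclusion.** The concern holds and is minor. As written, section 7.1 assigns a two-sample test to a primary endpoint measured twice in the same patients, with no second group defined anywhere in the plan. A paired test was probably intended.

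The size is zero if the changes are analysed. Only if before and after scores were compared as two samples would there be a loss. Across assumed correlations of 0.3 to 0.7, type I error would fall from 5% to between about 2.1% and 0.1%, and power would fall from 90% to between about 84% and 42%. At zero correlation there is no loss. These figures assume 20 complete pairs and borrow the effect size, alpha and power from the depression calculation.

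**What to change.** In section 7.1, replace the description of the SAFTEE test with a paired t-test, that is, a one-sample t-test on each patient's change between the two time points in Hypothesis 1.b. Reporting the mean change with its 95% confidence interval would be a useful addition, but the correction does not depend on it.

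If the table and attachments do not already say so, one further clause could state which assessment before TMS is the baseline, and that the later assessment is the one after the last session of the course, including for patients treated on a fourth day.

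The cost is one sentence, plus possibly one clause. The sample size, the visits and the 0.764 SD figure in section 7.2 are unchanged.

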- Patient will be given TMS motor threshold test to calibrate the machine for treatment, if not done at Visit 2. Following calibration, the designated TMS trained study team member or study RN will begin administering the first TMS treatment session under supervision of the study psychiatrist . Each treatment session will last approximately 50 minutes, and the patient will be given the opportunity to take a break between sessions. The patient will be scheduled to receive four, and may receive as many as seven, treatment sessions by the end of Visit 3.
- Following the final TMS session, study personnel will administer the SAFTEE, and PANAS.
- Following TMS, the family member/proxy will be instructed how to monitor the patient for safety, and he or she will be given contact information in case of unusually strong seizures. A hotel room will have been booked by study personnel prior to the study visit, if needed. The proxy will stay in the same room as the patient between all treatment days.
- The study Neurologist will be on call in case of unusual seizures.
-

6.5 *Visit 4: Second day of treatment*

- The proxy will bring the patient back to DHMC, and report to the Psychiatry Clinic for Visit 4.
- Research staff will administer the SAFTEE and PANAS. Seizure log will be reviewed.
- After completing assessments, the subject will begin the planned seven treatment sessions. Break times will be provided between sessions if desired.
- At the end of the final treatment session, research staff will:
 - Administer the SAFTEE and PANAS.
 - Remind the patient and proxy about contact and safety information before they depart.
- The study Neurologist will remain on call in case of unusually strong seizures.

6.6 *Visit 5: Third day of treatment*

- The proxy will bring the patient back to the Psychiatry Clinic for Visit 5.
- Research staff will administer the SAFTEE, PANAS. Seizure log will be reviewed.
- The patient will have four planned treatment sessions, but may receive as many as seven treatment sessions, with the opportunity to rest between trains.
- Once the final TMS treatment session is complete, a second dense-array EEG test will be conducted, which will last approximately one hour.
- After completion of the dense-array EEG, research staff will:
 - Administer the SAFTEE, PANAS, QIDS, and MoCA.
 - Debrief patient and proxy. Provide with safety information.
- Patient will be taken home by proxy*.

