8.1 Definitions

Unanticipated Problems Involving Risk to Subjects or Others

Any incident, experience, or outcome that meets all of the following criteria:

- Unexpected in nature, severity, or frequency (i.e. not described in study-related documents such as the IRB-approved protocol or consent form, the investigators brochure, etc.)
- Related or possibly related to participation in the research (i.e. possibly related means there is a reasonable possibility that the incident experience, or outcome may have been caused by the procedures involved in the research)
- Suggests that the research places subjects or others at greater risk of harm (including physical, psychological, economic, or social harm).

Adverse Event

An **adverse event** (AE) is any symptom, sign, illness or experience that develops or worsens in severity during the course of the study. Intercurrent illnesses or injuries should be regarded as adverse events. Abnormal results of diagnostic procedures are considered to be adverse events if the abnormality:

- results in study withdrawal
- is associated with a serious adverse event
- is associated with clinical signs or symptoms
- leads to additional treatment or to further diagnostic tests
- is considered by the investigator to be of clinical significance

Serious Adverse Event

Adverse events are classified as serious or non-serious. A **serious adverse event** is any AE that is:

- fatal
- life-threatening
- requires or prolongs hospital stay
- results in persistent or significant disability or incapacity
- a congenital anomaly or birth defect
- an important medical event

Important medical events are those that may not be immediately life threatening, but are clearly of major clinical significance. They may jeopardize the subject, and may require intervention to prevent one of the other serious outcomes noted above. For example, drug overdose or abuse, a seizure that did not result in in-patient hospitalization, or intensive treatment of bronchospasm in an emergency department would typically be considered serious.

All adverse events that do not meet any of the criteria for serious should be regarded as **non-serious adverse events**.

Adverse Event Reporting Period

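### Hypothesis 1.b is about the rate of adverse events, but Section 7.1 analyses the SAFTEE only as a change in the scale, which can hide treatment-emergent events, and plans no incidence analysis for non-serious ones

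*Combined protocol and SAP*

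**What the plan says.** Hypothesis 1.b (Section 2) reads "Treatment will not be associated with a higher rate of adverse events as measured by a modified Systematic Assessment for Treatment Emergent Events", with the instrument "given at baseline and immediately post-TMS". Primary endpoint 2 (Section 3.2) is "Change in significant side effects as assessed by the Systematic Assessment for Treatment Emergent Events"; the word significant is not defined. Section 8.1 says that an adverse event "is any symptom, sign, illness or experience that develops or worsens in severity during the course of the study".

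The analysis in Section 7.1 is one sentence: "The SAFTEE scale will be compared before and after TMS", using t-tests described as independent and applied to each patient's change from baseline. The same section plans occurrence rates with exact binomial intervals, but only for serious adverse events. It defines no treatment-emergent item, no patient-level incidence of non-serious events and no item table.

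The SAFTEE is given often. It is scheduled at screening (Visit 1b), before and after the sessions at Visit 3, and again at Visit 4, where the pre-session step is "Research staff will administer the SAFTEE and PANAS. Seizure log will be reviewed" (Section 6.5) and a second SAFTEE follows the last session. Visit 5 has one before the sessions and one after the final session and the EEG. Follow-up SAFTEEs come at 1 week and at 1, 3 and 6 months. Section 7.1 does not say which of these are used, or which one is the baseline.

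**The concern.** A rate counts patients or events in which something appeared or got worse. A mean change in a scale is worsening minus improvement. These patients enter with epilepsy, depression and, where prescribed, continuing medication, so some may report symptoms before the first session. Any of those symptoms that ease, through treatment or ordinary fluctuation, subtract from new side effects, and there is no control arm to separate the two.

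Timing matters as well. If the comparison is baseline against the end of treatment, as Hypothesis 1.b words it, a side effect that arises on day 1 or 2 and clears before the last Visit 5 SAFTEE does not enter the test, although it was collected.

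At stake is a primary safety endpoint in a study whose main purpose is safety: a result of no change would not establish that few patients had new events.

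**Working it through.** **1. The plan's own t-test figure.** The only one is in Section 7.2, for depression: n = 20, two-sided 0.05, power 0.90, detectable difference 0.764 SD of the changes. A paired t-test with 19 df and noncentrality d × √20 reaches 90% power at d = 0.7645, and has power 0.8997 at d = 0.764. The figure reproduces. No figure is given for the SAFTEE.

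**2. What the score estimates.** Let W be the points a patient gains from new or worse items and R the points lost from improved items. If the scale is a sum of items (an assumption, since scoring is not given), the change is D = W − R and mean(D) = mean(W) − mean(R). The incidence is the proportion of patients with W > 0. Mean(D) can be 0 or negative at any incidence, depending on R.

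**3. Illustration with assumed inputs.** Each patient has a 50% chance of gaining 2 points from a new side effect; every patient has a mean improvement m in other items; the residual SD of change is 2, 3 or 4; n = 20; two-sided one-sample t-test at 0.05; 20,000 simulated trials per setting. Expected mean change = 0.5 × 2 − m.

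| m | Expected mean change | Significant worsening (SD 2 / 3 / 4) | Significant improvement (SD 2 / 3 / 4) |
|---|---|---|---|
| 0 | 1.0 | 47.4% / 26.7% / 17.8% | 0.0% / 0.0% / 0.1% |
| 0.5 | 0.5 | 15.3% / 9.8% / 7.6% | 0.1% / 0.5% / 0.6% |
| 1 | 0 | 2.5% / 2.6% / 2.4% | 2.4% / 2.7% / 2.5% |
| 2 | −1.0 | 0.0% / 0.0% / 0.1% | 47.8% / 26.2% / 17.7% |

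The expected incidence is the same in every row: 10 of 20 patients. The result depends on the inputs: if 80% of patients gain 2 points and m = 1, worsening is detected in 22.2% / 12.4% / 9.1% of trials.

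**4. Timing.** After the first session there are five treatment-day SAFTEEs: after the Visit 3 sessions, before and after those at Visit 4, and before and after those at Visit 5. Comparing the pre-TMS Visit 3 SAFTEE with the last one at Visit 5 uses one of the five and leaves 5 − 1 = 4 out of the test.

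**5. What an incidence analysis would give.** Exact two-sided 95% limits for x of n are the 0.025 quantile of Beta(x, n − x + 1) and the 0.975 quantile of Beta(x + 1, n − x). With n = 20: 0/20 gives 0% to 16.8%; 4/20 gives 5.7% to 43.7%; 10/20 gives 27.2% to 72.8%.

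**6. Limit of a simple count.** If the modified SAFTEE keeps the 55 items of Section 3.3, five assessments make 55 × 5 = 275 item checks per patient. With an assumed independent background probability p per check, the chance of at least one new or worse item without any TMS effect is 1 − (1 − p)^275: 42% at p = 0.2%, 75% at 0.5% and 94% at 1%.

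**The case against.** The strongest reply is that Section 7.1 follows the hypothesis and the endpoint: 1.b is itself a before-and-after comparison, and endpoint 2 is a change. Nothing says that the modified SAFTEE contains depressive symptoms or is summed to one total. Section 7.1 uses t-tests in the plural and fixes no time points, and the post-TMS assessment in 1.b could mean the one after each day's sessions. Section 8.4 requires questioning about adverse events at every contact, and stopping rule 2c counts patients with significant side effects other than seizures.

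Much of this stands, and it rules out three stronger readings. A reader might infer that improving depression will cancel side effects; without the item list and scoring, the documents support only that it can. A reader might infer that days 1 and 2 are discarded by design; that holds only on the wording of 1.b, and Section 7.1 leaves it open. A reader might infer that events are lost or the safety question is abandoned; Section 8.4 and rule 2c capture them.

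The mismatch remains. Recording is not analysis, and Section 7.1 writes no rate for non-serious events. Even item-by-item t-tests would average improvement in some patients against worsening in others. It is also fair that a single-arm count cannot test whether a rate is higher; it can describe it.

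**Conclusion.** The concern holds in limited form. The stated hypothesis is about a rate, the planned analysis is a mean change, and no incidence of non-serious events is planned. The change score can hide treatment-emergent events, and on the narrower reading of the time points it omits transient ones. The gap is in the analysis, not in the collection of events.

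The size cannot be stated, because no SAFTEE event rate, item list or scoring is given. The illustration shows the mechanism only. Inputs can be chosen to make it look severe: with Poisson means of 2 gained and 2 lost items per patient, the expected change is 0 while 1 − e^−2 = 86% of patients have a new item, but that result lies wholly in the assumption. The point does not depend on which form of t-test is used.

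**What to change.** In Section 7.1 and endpoint 2 of Section 3.2:

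- Define a treatment-emergent SAFTEE event as an item new or worse than at the pre-TMS Visit 3 SAFTEE, at any later treatment-day assessment. Say which assessment closes the window for a patient who uses the optional fourth day in Section 6.6.
- Report the number and proportion of patients by item and by severity.
- Report the proportion with at least one significant treatment-emergent side effect, under a severity definition fixed before analysis, with the exact binomial method already planned for serious events.
- Keep the mean scale change as a supportive summary, stating its scoring and time points.
- State that, with no control arm, the counts are descriptive.

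Cost: no new visit, instrument or data, and a little more analysis. Changing endpoint 2 requires a protocol amendment, which Section 10 sends to the IRB. Repeated assessments pick up background symptoms, so the proportion with any new item will look less favourable and could approach its ceiling (step 6 of the working); it should not be read alone.

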6.1 Visit 1a: Initial Screening by Neurologist – Pre-enrollment

- Patient will review and sign informed consent.
- Initial screening will be done by a board-certified neurologist (, Visit 1a). Patient's history and physical will be taken, medications will be reviewed, seizure log, MOCA will be performed if time permits. All incomplete assessments may be done at Visit 1b.
- Subject will receive seizure log and instructions for its use.

6.2 *Visit 1b: Initial Screening by Psychiatrist – Pre-enrollment*

- Subsequent evaluation will be done by board-certified psychiatrist and research assistant Visit 1b). If the subject is unable to complete the full screening during Visit 1a, he or she may be scheduled for a second screening appointment with study psychiatrist and research assistant. At that time, diagnosis of medication-resistant depression will be confirmed; the MINI, QIDS, SAFTEE, PANAS MRI safety, TASS and ATHF will be performed. Seizure log data will be obtained.
- If time permits, Visit 2 procedures can be done at Visit 1b.

6.3 *Visit 2: Imaging and Baseline Neuropsychological Testing – Pre Enrollment*

- Patient will be report to the Advanced Imaging Center for MRI. MRI will last approximately one hour.
- After MRI is complete, patient will be brought to the EEG lab . A dense-array EEG will be conducted which will take approximately one hour.
- Patient will do neuropsychological and social-cognition testing, which will last approximately 2 hours. (QOLIE-31, RBANS and MAC-S)
- If time permits, TMS motor threshold may be done at Visit 2, so long as TMS treatment is scheduled to begin within one week. Otherwise, TMS motor threshold will be done at Visit 3.

6.4 *Visit 3: Enrollment and first day of TMS treatment*

- Patient will be brought to DHMC by their proxy for the first day of TMS treatment.
- Research staff will administer the QIDS, SAFTEE, and PANAS. Data will be obtained from the patient's seizure log.

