7.3 Subject Population(s) for Analysis

The patients successfully initiating the trial will be the analysis population to the safety outcomes. The patients completing the TMS will be the population for the secondary outcomes.

8 Safety and Adverse Events

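### Hypothesis 1.b claims no increase in adverse events on the SAFTEE, but the only planned analysis is a difference test without a confidence interval, and a non-significant result cannot support that claim.

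*Combined protocol and SAP*

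**What the plan says.** Section 2 states Hypothesis 1.b as a prediction of no harm: "Treatment will not be associated with a higher rate of adverse events", measured with a modified SAFTEE "given at baseline and immediately post-TMS". Section 3.2 lists change in side effects on the SAFTEE as the second primary endpoint.

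The whole SAFTEE analysis is one sentence in section 7.1: "The SAFTEE scale will be compared before and after TMS with independent t-tests", which the sentence goes on to base on each patient's own change. Section 5.2 makes the study single-arm: "All 20 patients with epilepsy and depression will be enrolled into the treatment group". Section 7.3 sets the safety population: "The patients successfully initiating the trial will be the analysis population to the safety outcomes".

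For SAEs, section 7.1 plans exact binomial confidence intervals, and section 7.2 discusses the upper limit of a one-sided interval. Section 7.2 has one t-test power statement, and it concerns depression scores. Neither section gives the SAFTEE an interval, significance level, sidedness, power or largest acceptable worsening.

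**The concern.** The hypothesis and the test point in opposite directions. The t-test takes no change as its null hypothesis, so a significant worsening would count against 1.b, while a non-significant result leaves 1.b undecided. A small sample produces non-significance easily, whether or not the SAFTEE truly worsens.

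What is at stake is the reading of a primary safety endpoint. Without an interval, a report of no significant change does not tell the reader how large an increase the data still allow. The weakness also grows as patients are lost: the fewer changes analysed, the more likely the result is to look reassuring.

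**Working it through.** **Inputs**
- n = 20, single arm (section 5.2).
- Test on within-patient changes. Section 7.1 calls the t-tests *independent* but bases them on each patient's change from baseline, so they are read here as one-sample (paired) tests.
- Two-sided 0.05. This is an assumption: section 7.2 states it for the depression comparison, and nothing is stated for the SAFTEE.
- Worsenings d of 0.3, 0.4 and 0.5 SD of the changes. These are illustrative; the documents give no value.

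**Method.** Power = P(|T| > t_crit), where T is noncentral t with n − 1 degrees of freedom and noncentrality d√n. For n = 20, √20 = 4.472, df = 19 and the two-sided 0.05 t_crit = 2.093.

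**Plan's own figure.** Section 7.2 says that 0.764 SD is detectable with power 0.90. Noncentrality = 0.764 × 4.472 = 3.417, which gives power 0.900. The plan's figure reproduces, so the method matches the one used there.

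**Same calculation for the SAFTEE, n = 20, two-sided 0.05**

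| d (SD of changes) | d√n | Power | Missed |
|---|---|---|---|
| 0.3 | 1.342 | 0.247 | 75% |
| 0.4 | 1.789 | 0.397 | 60% |
| 0.5 | 2.236 | 0.565 | 44% |

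**Other readings at d = 0.5**
- One-sided 0.05, n = 20: t_crit = 1.729, power 0.695, missed 30%.
- Two-sided 0.05, n = 16 (80% of 20): t_crit = 2.131, noncentrality 0.5 × 4 = 2.0, power 0.465, missed 54%.
- Literal two-sample test, 20 scores before and 20 after, with d now in raw-score SDs: df = 38, noncentrality 0.5 × √10 = 1.581, power 0.338, missed 66%.

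**What an upper limit would give.** One-sided 95% limit = observed mean change + t(0.95, n − 1)/√n × SD of the changes.
- n = 20: 1.729/4.472 = 0.387, so mean + 0.39 SD.
- n = 16: 1.753/4 = 0.438, so mean + 0.44 SD.

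If the observed mean change were exactly zero in 20 patients, the data would exclude only increases above 0.39 SD.

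**The case against.** A reader might infer that the sponsor will treat p>0.05 as proof of safety. The documents do not say so; they give no rule for reading a non-significant SAFTEE result. What can be said is that they state a no-increase hypothesis and a single test, and that this test cannot establish the hypothesis.

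Nor does the whole safety judgement rest on this one p-value. Section 7.1 gives intervals for SAEs. Section 8.7 stops the study if more than three patients have significant side effects other than seizures. Section 4.2.1 provides for discontinuation for intolerance, and section 8.4 requires adverse-event questioning at each contact. These safeguards are real and narrow the consequence, but none of them bounds the SAFTEE change or tests 1.b. The study monitoring plan (Attachment E) is not among the documents reviewed.

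The miss rates depend on a borrowed significance level and on effect sizes that nothing in the plan ties to clinical relevance. That objection stands, so they are shown as a range. The logical point depends on neither.

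Two stronger remedies are tempting, but the documents do not support requiring them.
- **A pass/fail margin.** The plan offers no basis for a value. With a margin of 0.5 SD and a true change of zero, 20 patients would meet it only 70% of the time at one-sided 0.05, so a harmless treatment would often fail. For a pilot, an estimate with an interval is enough.
- **An untreated reference.** The SAFTEE is also given at Visit 1b (section 6.2: "the MINI, QIDS, SAFTEE, PANAS MRI safety, TASS and ATHF will be performed"), before the pre-treatment SAFTEE at Visit 3. A reader might take the change between them as a control. The interval between those visits is unspecified, and patients are selected at screening on depression scores, which may distort that change. It is at most an optional descriptive display.

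**Conclusion.** The concern holds as a mismatch between hypothesis and analysis. Section 7.1 can produce evidence against 1.b but none for it, and it leaves the SAFTEE without the interval that SAEs receive.

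The practical size is considerable. A worsening of 0.5 SD of the changes would be missed 44% of the time at two-sided 0.05 with 20 patients, and between 30% and 54% under the one-sided and 16-patient readings. Smaller worsenings are missed more often than not. These figures assume a test on within-patient changes and effects measured in SDs of those changes. If half an SD meant the raw-score SD, the 44% would apply at a pre–post correlation of 0.5, with 57% at 0.3 and 22% at 0.7.

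The finding does not show that the study would be declared safe on a null result, or that patients lack other safety monitoring.

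**What to change.** In section 7.1:
1. Report the mean SAFTEE change from the pre-TMS baseline to immediately post-TMS with a one-sided 95% upper confidence limit, naming the two visits used. The SAFTEE is given before treatment at Visits 1b and 3 and after sessions at Visits 3, 4 and 5. At n = 20 the limit is the observed mean plus 0.39 SD of the changes. This extends to the SAFTEE the interval approach already planned for SAEs.
2. Word the conclusion on 1.b as: an increase larger than X is excluded, where X is that limit.
3. State that p>0.05 is not evidence for 1.b.
4. Replace *independent* with *paired* or *one-sample*, and state the level and sidedness.

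A formal margin is optional. If one is used, it must be fixed before any post-TMS SAFTEE data are seen. Fixing it only before data lock would protect little in an unblinded single-arm study. The Visit 1b to Visit 3 change is not part of the required fix.

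Cost: a few lines of SAP wording and one line of output, with no new patients, assessments or change to treatment. The downside is that the claim becomes a bounded increase instead of no increase.
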